## 5. Study Design

### 5.1. Overall Design

Study ITSB is a Phase 3, prospective, randomized, outpatient, multinational, multicenter, parallel, active-controlled study, conducted in children and adolescent patients with T1D currently using a multiple-daily-injection (MDI) regimen. In 2 of the treatment groups, LY900014 or Humalog will be administered immediately (0 to 2 minutes) prior to each meal in a double-blind manner. A third open-label treatment group consists of LY900014 administered up to 20 minutes after the start of a meal (LY900014+20). It is not possible to blind this treatment group as it uses a different injection timing. The study is designed to demonstrate noninferiority of LY900014 when compared with Humalog in change from baseline to Week 26 in HbA1c, when both are administered at the start of the meal. The study includes a 1-week screening with a 4-week lead-in period followed by a 26-week treatment period and a 2-week safety follow-up period.

The purpose of the lead-in period is to obtain blood glucose (BG) values along with basal and prandial insulin doses to assess basal and mealtime insulin dosing and to determine baseline hypoglycemia rates. Basal insulin should be titrated by the patient or caregiver during the lead-in period, in anticipation of increased activity or individual patient needs, so as to achieve or maintain glucose targets ([Table ITSB.4](#)) with an emphasis on the pre-breakfast BG.

Investigators will have access to a patient's glucose values; so, they may assist patients and caregivers with appropriate basal adjustments. The lead-in will also allow patients and caregivers to become familiar with the patient study diary and the documentation required throughout the study. Patients treated with insulin glargine U-100 once a day (QD) or twice a day (BID), insulin detemir U-100 QD or BID or insulin degludec U-100 QD will be eligible for inclusion in the trial. At Visit 2, patients will continue their allowed study basal insulin regimen at the same dosing frequency (QD or BID). Patients should remain on the same basal insulin throughout the study; switching brands should be avoided when possible.

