##### Every day

- Answering study diary questions for all hypoglycemia events
- Obtaining glucose value before meals and at bedtime

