#### **10.3.4. Safety Analyses**

Safety measures will include AEs, hypoglycemia, vital signs and weight, treatment exposure, laboratory measures, and antibodies to insulin lispro. Analyses will be performed on data collected from randomization through Visit 801 for both treatment groups.

Events that are newly reported after the first dose of IP or reported to worsen in severity from baseline will be considered treatment-emergent AEs (TEAEs). The Medical Dictionary for Regulatory Activities (MedDRA) lowest level term (LLT) will be used in the treatment-emergent assessment. The maximum severity for each LLT during the baseline period will be used as baseline severity.

The SAEs, AEs reported as reason for discontinuation from the IP or study, and TEAEs will be summarized in tables using the MedDRA PT, sorted by decreasing frequency within the LY900014 treatment group. The TEAEs will also be summarized by PT sorted by decreasing frequency within SOC for all TEAEs and by maximum severity. For events that are specific to only 1 sex, the denominator and computation of the percentage will include only patients from

the given sex. The number and proportion of patients with at least 1 event for each type of event will be summarized and compared between treatment groups using Fisher's exact test.

Hypoglycemia rates will be summarized for periods of 30 days, 1 year, and 100 years (severe hypoglycemia only). The rate of severe hypoglycemia per 100 years will be compared between treatment groups using the empirical method (details will be described in SAP). For each of the other categories of hypoglycemia, the number of hypoglycemia events during a specific period after randomization (for example, Weeks 0 to 12 of treatment period) will be analyzed by using a negative binomial regression model. The model will include treatment and age group as covariates. An offset defined as the log transformation of treatment exposure in the specific period (days)/365.25 days (or 30 days) will be included in the model to estimate the rate of hypoglycemia per year (or per 30 days). The proportion of patients with at least 1 hypoglycemic event in each category during a specific period after randomization will be analyzed using a logistic regression model including treatment and age group as covariates.

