Rate of hypoglycemic events (per patient per year) All Documented ^a Nocturnal ^a Non-Nocturnal (Documented and occurred between waking and bedtime) ^a	0-12, 0-26weeks	Negative binomial regression with treatment and age group as covariates, log (exposure/365.25 days) as the offset in the model.
Incidence of hypoglycemic events All Documented ^a Nocturnal ^a Non-Nocturnal (Documented and occurred between waking and bedtime) ^a	0-12, 0-26weeks	Logistic regression with treatment and age group as covariates.
Rate of post-dose hypoglycemic events (per patient per year) for all 3 main meals All Documented ^a	≤1, ≤2, ≤4, >4, and >2 to ≤4 hours after start of prandial insulin dose within 0-12, 0-26,weeks	Negative binomial regression with treatment and age group as covariates, log (exposure/365.25 days) as the offset in the model.
Incidence of post-dose hypoglycemic events for all 3 main meals All Documented ^a	≤1, ≤2, ≤4, >4, and >2 to ≤4 hours after start of prandial dose within 0-12, 0-26,weeks	Logistic regression with treatment and age group as covariates.
Rate of severe hypoglycemic events (per patient per 100 years)	0-12, 0-26weeks	Exposure adjusted rate 100 years (calculated by total number of events divided by total exposure for individual patients) will be provided and the empirical method (see Appendix 1 for details) will be used for treatment comparison.
Incidence of severe hypoglycemic events	0-12, 0-26weeks	Proportion of patients with severe hypoglycemia will be reported. The treatment comparison will be based on a logistic regression model with treatment and age group as covariates.

^a All documented hypoglycemia and the subcategories based on the thresholds of blood glucose ≤70 mg/dL and blood glucose <54 mg/dL will be analyzed.

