Appendix 2.4. Primary CGM Outcome and Methodology

The primary outcome of the CGM addendum is the iAUC0-2hr after meals obtained from up to 10 days of CGM use at Week 26. The derivation of the iAUC0-2hr for each visit is outlined in [Appendix 2.8](#).

An ANCOVA model with treatment, type of basal insulin, hemoglobin A1c (HbA1c) stratum [$\leq 8.0\%$ or $> 8.0\%$], and age group as fixed effects and baseline as a covariate will be used for treatment group comparison. At Week 26, the treatment difference and LS mean of the difference estimated from the model will be provided.

If the percentage of the patients with missing baseline values is higher than 20% of the CGM Population, a constrained longitudinal data analysis model (Liu et al. 2009; Lu 2010) will be used instead. An unstructured covariance structure will be used to model the within-patient

errors. If this analysis fails to converge, the following covariance structures will be tested in order:

- compound symmetry with heterogeneous variances
- compound symmetry without heterogeneous variances.
- First order autoregressive

The first covariance structure that converges will be used. The Kenward–Roger approximation will be used to estimate denominator degrees of freedom.

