Appendix 2.5. Secondary CGM Variables and Analysis

The following variables will be derived from the original data collected through the CGM device and will be compared LY900014, LY900014+20 and Humalog at Week 26 using the similar model as the primary analysis in [Appendix 2.4](#):

- incremental AUC 0-2 hours after the start of meals (across all three main meals)
- duration (in minutes) and percentage of time with glucose values between 70 and 180 mg/dL (3.9 and 10.0 mmol/L) (both inclusive) during daytime (defined as 0600 to midnight), normalized to a 24-hour period
- average glucose excursions 0 to 1 hour after the start of meals (across all 3 main meals)
- average glucose excursions 0 to 2 hours after the start of meals (across all 3 main meals)
- average glucose excursions 0 to 3 hours after the start of meals (across all 3 main meals)
- average glucose excursions 0 to 4 hours after the start of meals (across all 3 main meals)
- duration (in minutes) and percentage of time with glucose values <54 (3.0 mmol/L) normalized to a 24-hour period
- duration (in minutes) and percentage of time with glucose values <70 mg/dL (3.9 mmol/L) normalized to a 24-hour period
- duration (in minutes) and percentage of time with glucose values >180mg/dL, (10.0 mmol/L) normalized to a 24-hour period
- blood glucose risk index during daytime (0600 to midnight)

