Appendix 2.6. Additional Analyses

The following key efficacy and safety outcomes collected in the main study (not through CGM addendum) will be analyzed using the CGM Population:

- HbA1c at Week 26
- incidence and rate of documented hypoglycemic events from Week 0 to Week 26
- incidence and rate of nocturnal hypoglycemic events from Week 0 to Week 26
- incidence and rate of non-nocturnal hypoglycemic events from Week 0 to Week 26s
- incidence and rate of severe hypoglycemic events from Week 0 to Week 26

- change from baseline in total, basal and prandial insulin dose, and the ratio of prandial and total insulin dose at Week 26

The analysis methods for the above outcomes will be the same as those specified in Section 5.

Proportion of patients who have achieved the guidance (Battelino et al. 2019) recommended CGM targets of glycemic control (see Table APP.2.2) at Week 26 will also be summarized by treatment and analyzed using logistic regression model with treatment, age group and baseline as covariates.

Table APP.2.2. Guidance Recommended CGM Targets of Glycemic Control

Percentage of time with sensor glucose (24-hour)	Guidance Recommendation
target range	
70-180 mg/dL (3.9-10.0 mmol/L, both inclusive)	>70%
hypoglycemia range	
<70 mg/dL (3.9 mmol/L)	<4%
<54 mg/dL (3.0 mmol/L)	<1%
hyperglycemia range	
>180 mg/dL (10.0 mmol/L)	<25%
>250 mg/dL (13.9 mmol/L)	<5%

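### The main hypoglycemia rate models leave out the lead-in rate that the trial collects, which costs precision when events are frequent and a patient's rates are correlated over time

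*SAP*

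**What the plan says.** The first rate row of Table ITSB.5.4 (SAP 5.12.4.1) covers all documented, nocturnal and non-nocturnal events, over Weeks 0-12 and 0-26, at both glucose thresholds (at or below 70 mg/dL, and below 54 mg/dL). The method is "Negative binomial regression with treatment and age group as covariates, log (exposure/365.25 days) as the offset in the model". Protocol 10.3.4 matches it: "The model will include treatment and age group as covariates". Neither document puts a lead-in rate into a hypoglycemia model, as main or supportive analysis.

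The covariate exists. Protocol 5.1 says that the lead-in gathers glucose values and insulin doses "to assess basal and mealtime insulin dosing and to determine baseline hypoglycemia rates". Protocol 9.1.5 lists among the daily duties of the patient or caregiver "Answering study diary questions for all hypoglycemia events". Diaries go out at Visit 2 and come back at Visit 4 (Schedule of Activities). SAP Table ITSB.5.2 names Visits 2 to 4 as the baseline for the treatment-period hypoglycemia analysis.

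The same SAP adjusts for baseline when hypoglycemia is measured by CGM. Appendix 2.5 lists "duration (in minutes) and percentage of time with glucose values <70 mg/dL (3.9 mmol/L) normalized to a 24-hour period", with a counterpart below 54 mg/dL, and sends both to a model like that of Appendix 2.4, which has treatment, type of basal insulin, HbA1c stratum "and age group as fixed effects and baseline as a covariate will be used for treatment group comparison". In Appendix 2.6, meeting the CGM targets, which include hypoglycemia targets, is "analyzed using logistic regression model with treatment, age group and baseline as covariates".

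**The concern.** A baseline is defined for an analysis whose model never uses it. A child's earlier event rate is a natural predictor of the later one, and in a count model a good predictor takes up between-patient variation that would otherwise sit in the dispersion. Leaving it out gives up precision that the families' lead-in diaries could supply. This matters most for LY900014+20 against Humalog, where one arm has only about 142 patients.

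The stakes are limited. The rate of documented hypoglycemia is Objective 5, one of the other secondary objectives, and SAP 5.5 makes no multiplicity adjustment for it. The point covers the first rate row only. It makes no claim about post-dose rates, the logistic incidence models or severe hypoglycemia.

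**Working it through.** **Inputs from the documents (protocol 10.1, 5.1 and Schedule of Activities).** 240/0.85 = 282.4, so 283 per blinded arm; 120/0.85 = 141.2, so 142 in LY900014+20; total 283 + 283 + 142 = 708, as stated. The lead-in is 28 days, treatment is 182 days, and 15% drop out. The documents give no hypoglycemia rate, dispersion or power to reproduce.

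**Assumed inputs.** Rates of 5, 10, 30 and 60 events per patient-year; variance of the log rate between patients 0.7, so dispersion exp(0.7) - 1 = 1.01; correlation between lead-in and on-treatment rates of 0.3, 0.6 or 0.8; patient rates lognormal, or gamma with the same dispersion.

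**Planned interval by hand, 142 against 283 at 30 per year.** If early stoppers leave halfway on average, mean exposure is 0.85 × 182 + 0.15 × 91 = 168 days, or 168 × 30/365.25 = 13.8 events per patient. Then SE(log rate ratio) = sqrt[(1/13.8 + 1.01)(1/142 + 1/283)] = sqrt(1.082 × 0.01058) = 0.107. The 95% interval is the estimate multiplied and divided by exp(1.96 × 0.107) = 1.23.

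**Simulated gain.** Negative binomial maximum likelihood, age group in both models, no true effect, 1,500 trials per setting. The covariate is log((lead-in events + 0.5)/lead-in exposure). Percentage reductions at correlations 0.3 / 0.6 / 0.8:

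| Events per patient-year | Model SE, lognormal | Model SE, gamma | SD of estimate, lognormal | SD of estimate, gamma |
|---|---|---|---|---|
| 5 | 0.4 / 2.1 / 4.0 | 0.5 / 2.4 / 4.6 | 1.4 / 3.9 / 8.5 | 0.3 / 1.6 / 4.1 |
| 10 | 0.8 / 3.8 / 7.3 | 1.0 / 4.5 / 8.6 | 1.7 / 6.0 / 13.7 | 0.7 / 2.8 / 5.9 |
| 30 | 1.7 / 7.8 / 15.1 | 1.8 / 8.1 / 16.3 | 2.9 / 12.7 / 22.0 | 0.5 / 7.3 / 15.3 |
| 60 | 2.3 / 10.5 / 20.5 | 2.2 / 10.2 / 21.0 | 3.4 / 15.6 / 28.6 | 1.7 / 8.2 / 20.6 |

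Monte Carlo error of the SD columns is at most 1.6 points. The mean log rate ratio stayed within 0.007 of zero with and without the covariate, so there is no sign of bias. The gain fades for rarer events because the lead-in says little: at 5 per year a patient expects 5 × 28/365.25 = 0.38 lead-in events.

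Subsets at 30 per year overall, using the all-documented covariate: the model SE falls 1-11% for nocturnal events (assumed 15% of events) and 2-16% for non-nocturnal events.

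**Second check.** 283 against 283, true rate ratio 0.9, gamma, dispersion 0.5 or 1.0, about 100 trials per setting. Planned interval width over adjusted width at correlations 0.3 / 0.6 was 1.02 / 1.10-1.11 at 60 per year, 1.01-1.02 / 1.05-1.07 at 20 and 1.00-1.01 / 1.01-1.03 at 5. At 1 per year it never exceeded 1.01.

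**Reported interval factor for LY900014+20 against Humalog, 30 per year** (400 to 500 trials per setting):

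| Patient rates | Planned | With covariate, 0.3 / 0.6 / 0.8 |
|---|---|---|
| Gamma | 1.235 | 1.23 / 1.21 / 1.19 |
| Lognormal | 1.19 | 1.19 / 1.175 / 1.16 |

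Under lognormal rates the spread of the planned estimate calls for about 1.23, not 1.19. The reported factor implies a fitted dispersion of only (ln 1.19/1.96)²/0.01058 - 1/13.8 = 0.67, against 1.01. The implied null rejection is 2 × [1 - Φ(1.96 × ln 1.19/ln 1.23)] = 2 × [1 - Φ(1.65)], about 10%; the simulation gave 9-11%. Across the four rates, lognormal rejection was 7.2-10.9% without the covariate and 6.3-9.9% with it. Under gamma it was 4.4-6.1% and 4.5-6.5%.

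**The case against.** A reader might infer that the planned interval is simply wider than the data allow. The documents do not support that, because they say nothing about how rates vary between patients. Under lognormal rates the planned interval (1.19) is narrower than a correctly sized adjusted one, which would need about 1.22 at correlation 0.3 and 1.21 at 0.6. In that case under-coverage is the larger problem and the covariate leaves most of it. This objection stands, so the claim has to be about the precision of the estimate.

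The size is also assumed throughout, and a low correlation is plausible. Patients switch prandial insulin and titrate basal insulin in the lead-in, and protocol 5.1 adds that "The lead-in will also allow patients and caregivers to become familiar with the patient study diary". At correlation 0.3 the interval hardly moves. The analyses below 54 mg/dL and over Weeks 0-12 were not simulated. Both limits stand.

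The CGM comparison is weaker than it looks. Those outcomes come from a device in an addendum, and Appendix 2.6 sends event rates in that population back to the Section 5 methods. It shows that the SAP accepts baseline adjustment for hypoglycemia outcomes, and no more.

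Last, the post-dose row uses the same model, so changing only the first row leaves Objectives 4 and 5 with different adjustment. That is a real cost in consistency, but it does not remove the gain.

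**Conclusion.** The omission is certain from the text, and the direction is firm: the rate ratio is unbiased, but it is estimated less precisely than it could be when events are frequent and lead-in and on-treatment rates are at least moderately correlated. The size is conditional. At an assumed 30 events per patient-year, the model SE reductions of about 2%, 8% and 15-16% equal roughly 4% (1/0.98²), 18% (1/0.92²) and 38-42% (1/0.85² to 1/0.84²) more patients. For rare categories the gain is small.

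A reader might go further and call the planned analysis biased, invalid or inconsistent between documents. None of these follows: allocation is randomized, protocol and SAP specify the same model, and no gated claim uses it. This is an optional gain in precision for an objective without multiplicity control.

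**What to change.** Before unblinding, add one covariate to the models in the first rate row of Table ITSB.5.4: log((lead-in events + 0.5)/lead-in exposure).

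- Count documented lead-in events at or below 70 mg/dL over Visits 2 to 4, with the 30-minute merging rule of SAP 5.12.4.1.
- Use the same covariate for every category in the row.
- Where lead-in data are absent, use the pooled mean plus a missing indicator.
- Keep the treatment plus age-group model as supportive.
- State whether the covariate carries into the analyses that reuse these models: TEADA subgroups (SAP 5.12.7.1), hypoglycemia subgroups (5.13.2) and the CGM population (Appendix 2.6).

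The cost is one derived variable, a second set of model runs (more if the covariate carries over) and a SAP change with a stated justification. Protocol 10.3.1 and SAP 5.1 allow this route for changes that do not touch a principal feature of the protocol. No new data are needed. If unblinding has already happened, label the adjusted model post hoc.

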## 10. Statistical Considerations

### 10.1. Sample Size Determination

Approximately 708 patients will be randomized in order that 600 patients complete the study through the primary endpoint at Week 26.

Patients will be randomized in a 2:2:1 ratio to double-blind LY900014 dosed 0 to 2 minutes before meals, double-blind Humalog dosed 0 to 2 minutes before meals, or open-label LY900014 dosed up to 20 minutes after the start of a meal. Stratification will be by country, HbA1c stratum ( $\leq 8.0\%$ ,  $> 8.0\%$ ), type of basal insulin (insulin glargine, insulin detemir, or insulin degludec), and age group (1 to  $< 12$  years, 12 to  $< 18$  years).

Assuming a NIM of 0.4%, no true difference between treatment groups and an SD of 1.1%, 240 completers for each double-blind treatment group will provide greater than 95% power to show noninferiority between LY900014 and Humalog using the upper limit of a 2-sided 95% CI (LY900014–Humalog). This sample size also has more than 80% power to show noninferiority between LY900014 and Humalog using a 0.3% NIM at 26 weeks.

With the assumption a difference no larger than 0.07% between treatment groups and a SD of 1.1%, 240 completers of double-blind Humalog dosed 0 to 2 minutes before meals and 120 completers of open-label LY900014 dosed up to 20 minutes after the start of a meal will provide approximately 76% power to show noninferiority between open-label LY900014+20 and double-blind Humalog using a NIM of 0.4%.

Assuming a 15% dropout rate during 26 weeks of treatment, approximately 708 patients (283 patients in each double-blind treatment group and 142 patients in the open-label treatment group) will need to be randomized.

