- For the 7-point self-monitored blood glucose (SMBG) profiles, the profiles measured after the first IP dose date and prior to the last IP dose date will be considered as data on IP.

Unless otherwise noted, all tests of treatment effects will be conducted at a 2-sided alpha level of 0.05, and confidence interval (CI) will be calculated at 95%, 2-sided. All tests of interactions between treatment groups and other factors will be conducted at a 2-sided alpha level of 0.05. Countries in similar geographic regions with fewer than 10 patients, based on all Randomized Population, will be pooled to achieve a pooled country of at least 10 patients. All analyses using country in the model will use a pooled country, unless otherwise specified. The final pooling by country and geographic region will be finalized prior to data lock.

[Table ITSB.5.2](#) shows the definition of baseline and post-baseline for each variable to be analyzed. The baseline variables are derived from the evaluable data during the baseline period.

Table ITSB.5.2. Baseline and Postbaseline Definitions and Patient Population by Study Period and Type of Analysis

Study Period/Analysis	Patient Population	Baseline Observations	Post-Baseline Observations
Lead-In Period			
HbA1c ANCOVA	All Randomized Patients	Visit 1	Visit 4 prior to initiation of IP
Basal, bolus, and total insulin doses, and bolus/total insulin dose ratios continuous analysis	All Randomized Patients	Not applicable	Visit 3-4
TEAE	All Enrolled Patients	Prior to first dose of open-label insulin lispro (or Visit 2 date if the dose date is missing)	The entire lead-in period after first dose of open-label insulin lispro and prior to the first dose of IP (or Visit 4 if the dose date is missing)
26-Week Treatment Period (including Safety Follow-Up Visit where applicable)			
HbA1c ANCOVA (ITT estimand)	All Randomized Patients	Last of Visits 1-4	Visit 15 with imputation for patients who discontinue study prior to Visit 15
HbA1c MMRM (efficacy estimand)	All Randomized Patients with a baseline and at least one post-baseline observation while on IP	Last of Visits 1-4	Visits 7, 10, and 15 prior to discontinuation of IP
HbA1c categorical analysis longitudinal logistic regression	All Randomized Patients with a baseline and at least one post-baseline observation while on IP	Last of Visits 1-4	Visits 7, 10, and 15 prior to discontinuation of IP

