5.2. Adjustments for Covariates

Stratification factors of this study include country, HbA1c stratum ($\leq 8.0\%$, $>8.0\%$), type of basal insulin at randomization (insulin glargine, detemir or degludec), and age group (1 to <12, 12 to <18 years). Stratification factors will be entered into the interactive web-response system (IWRS) for randomization and also collected in the database by electronic case report form (eCRF) or central laboratory. The analysis models will use the stratification factors as collected in the database.

For the primary analysis of HbA1c, the stratification factor of HbA1c stratum will not be included. Instead, the continuous value of baseline HbA1c will be included in the analysis models.

Other efficacy analyses will include the stratification factors as noted in Sections 5.11 and 5.12.

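### The hypoglycemia models adjust for only one of the four randomization strata, without a stated reason; adding HbA1c stratum and basal insulin type would be a minor, nearly free improvement

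*SAP*

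**What the plan says.** SAP 5.2 names the strata ("Stratification factors of this study include country, HbA1c stratum", then basal insulin type and age group). It says that other efficacy analyses include them as Sections 5.11 and 5.12 specify. Protocol 7.2 and 10.1 list the same four factors.

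In SAP Table ITSB.5.4 (Section 5.12.4.1):
- The rate rows for documented, nocturnal, non-nocturnal and post-dose events use "Negative binomial regression with treatment and age group as covariates", with log exposure as the offset.
- The matching incidence rows use "Logistic regression with treatment and age group as covariates".
- Severe-event rate uses the empirical method of Appendix 1. Severe-event incidence uses the same two-term logistic model.

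Protocol 10.3.4 agrees: "The model will include treatment and age group as covariates". Neither document explains why age group is kept and the other three strata are not.

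Rate and incidence of post-dose and of documented hypoglycemia are secondary objectives 4 and 5. They are tested at the general two-sided 0.05 level (SAP 5.1), with no multiplicity adjustment (SAP 5.5).

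**The concern.** When randomization is balanced within strata that predict the outcome, a model that ignores those strata leaves their variation in the error term. In the negative binomial model it goes into the dispersion, and the reported standard error of the log rate ratio is larger than it needs to be.

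Elsewhere the plan does carry these factors. The insulin-dose and SMBG models add HbA1c stratum to a model that already has basal type (SAP 5.11.5). The CGM models, including those for time in the hypoglycemic ranges, contain basal type, HbA1c stratum and age group (SAP Appendix 2.4 and 2.5). SAP 5.13.2 also analyzes documented hypoglycemia at the 70 mg/dL threshold by HbA1c stratum and by basal type.

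What is at stake is some efficiency in the comparisons for objectives 4 and 5. Validity is not in question.

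**Working it through.** **1. What the plan's own figures cover.** Protocol 10.1 sizes the trial on HbA1c alone (SD 1.1%, two-sided 0.05). Power = Φ(δ/SE − 1.96):
- 240 vs 240: SE = 1.1 × √(2/240) = 0.1004. Margin 0.4: Φ(3.98 − 1.96) = 0.978; stated "greater than 95% power to show noninferiority between LY900014 and Humalog". Margin 0.3: Φ(2.99 − 1.96) = 0.848; stated "more than 80% power to show noninferiority between LY900014 and Humalog using a 0.3% NIM at 26 weeks".
- 240 vs 120, δ = 0.4 − 0.07 = 0.33: SE = 1.1 × √(1/240 + 1/120) = 0.1230; Φ(2.68 − 1.96) = 0.765; stated as about 76%.
- Dropout 15%: 240/0.85 gives 283 and 120/0.85 gives 142; 283 + 283 + 142 = 708.

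All of these reproduce. None concerns hypoglycemia: no event rate, dispersion, incidence, stratum effect, power or interval width is stated for objectives 4 and 5.

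**2. Which strata are in the models.** Of the four randomization factors, the models contain age group and omit country, HbA1c stratum and basal type. Adding HbA1c stratum (1 parameter) and basal type (2 parameters) costs 3 degrees of freedom.

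**3. Size, under assumed inputs.** Simulation of 283 vs 283 patients, balanced within HbA1c stratum × basal type × age, 150 replicates per row, no treatment effect. Assumed: about 25 events per patient over 26 weeks, dispersion 0.8, incidence about 70%, HbA1c strata 50/50, basal types 60/10/30. Each entry gives the median SE as planned (treatment + age), the median SE with both strata added, and the interval-width ratio (from unrounded values). The effects are rate ratios in the rate model and odds ratios in the incidence model.

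| HbA1c-stratum effect, degludec effect | Rate model: log rate ratio | Incidence model: log odds ratio |
|---|---|---|
| 1, 1 | 0.0766 → 0.0764 (0.998) | 0.1842 → 0.1846 (1.002) |
| 1.25, 1.1 | 0.0772 → 0.0767 (0.993) | 0.1840 → 0.1847 (1.004) |
| 1.5, 1.2 | 0.0789 → 0.0769 (0.974) | 0.1841 → 0.1854 (1.007) |
| 2, 1.5 | 0.0827 → 0.0770 (0.930) | 0.1825 → 0.1861 (1.020) |
| 3, 2 | 0.0915 → 0.0773 (0.845) | 0.1814 → 0.1892 (1.043) |

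Hand check of the adjusted rate SE: √(2 × (1/25 + 0.8)/283) = 0.077.

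**4. Rates.** The interval narrows by 0.2% to 2.6% for null to modest effects (first three rows), 7% for effects of 2 and 1.5, and about 15% for 3 and 2. A second simulation used all 708 patients at 2:2:1, with dispersion 0.8 at 40 events per year and 1.5 at 4 events per year. Its SE ratios were 0.991 and 0.996 at an HbA1c-stratum rate ratio of 1.3; 0.980 and 0.991 at 1.5; and 0.945 and 0.971 at 2.0 with a basal rate ratio of 0.8. The most favorable of these equals about 12% more patients (1/0.945² = 1.12), but it needs the strong effect and the smaller dispersion.

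**5. Incidence.** The odds-ratio interval widens by 0.2% to 4.3% on adjustment, because the adjusted odds ratio is a different, conditional quantity with a larger standard error. To see whether anything is gained, a further simulation (283 vs 283, 1200 runs, treatment odds ratio 1.6, reference incidence about 50%) gave:

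| HbA1c-stratum OR, degludec OR | Treatment OR, planned vs adjusted | Power | SE of standardized risk difference |
|---|---|---|---|
| 1.5, 1.2 | 1.60 vs 1.61 | 77.6% → 78.9% | −0.8% |
| 2, 1.5 | 1.57 vs 1.60 | 74.9% → 76.2% | −2.0% |
| 3, 2 | 1.54 vs 1.61 | 71.0% → 74.3% | −4.8% |

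Other runs under similar assumptions gave gains of 0 to 3 points of power.

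**The case against.** The strongest reply is that nothing is wrong. The covariate set is prespecified, and protocol and SAP agree on it. SAP 5.2 leaves the choice to each section. Hypoglycemia sits among the safety analyses, where the laboratory and vital-sign models carry no strata at all (SAP 5.12.5, 5.12.6). The dose, SMBG and CGM models are for continuous outcomes. All of this stands: age group alone is a permissible choice.

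It is also said that SAP 5.13.2 already covers the point. It does so only in part. It brings in each factor with its treatment interaction, as a subgroup analysis at the 70 mg/dL threshold, and leaves the main comparison unchanged. Nor does being listed as a subgroup show that a factor is prognostic; region, dosing plan and CGM use are listed too.

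Two practical objections have weight. First, country is a stratum as well. However, a pooled country may hold as few as 10 patients (SAP 5.4), about 4, 4 and 2 per arm at 2:2:1, which invites separation in a logistic model. The CGM model likewise uses basal type, HbA1c stratum and age group without country. Second, extra terms may fail in sparse categories such as events below 54 mg/dL or within one hour of a dose, with 142 patients in the open-label arm. A fallback rule is therefore needed.

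A reader might infer two stronger things. One is that the planned intervals are wider than the design allows. The documents set no precision target for objectives 4 and 5, and for incidence the planned odds-ratio interval is the narrower one. The other is that the planned odds ratio is biased toward 1. The shift is non-collapsibility: the two models estimate different odds ratios.

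**Conclusion.** The hypoglycemia rate and incidence models adjust for one of four randomization strata without a stated reason, and adding two more that are already collected is worthwhile. The planned inference is valid; if the omitted strata are prognostic it is slightly conservative, and it does not lean toward a false difference.

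For rates, the gain is about 0-3% in interval width for null to modest stratum effects and about 7% or more only for strong ones, with essentially no loss if there is no effect. For incidence, it is a small rise in power and a slightly narrower risk-difference interval. All sizes rest on assumed event rates, dispersion, incidence and stratum effects, so only direction and rough size should be used. This is a minor, free improvement.

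**What to change.** In SAP Table ITSB.5.4, for documented, nocturnal, non-nocturnal and post-dose hypoglycemia:
- Add HbA1c stratum (≤8.0%, >8.0%) and type of basal insulin to the negative binomial rate models.
- Add the same two factors to the logistic incidence models. Report a standardized risk difference (or ratio) and state that the adjusted odds ratio is conditional on these factors.
- Keep the age-only model for severe-event incidence. Prespecify a fallback to it for any sparse category where the adjusted model fails to converge or shows separation.
- Give the reason for the covariate set, including why country is left out.

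Align protocol 10.3.4, or record the change and its justification in the SAP; protocol 10.3.1 requires an amendment only where a principal feature changes. The cost is SAP wording, three model degrees of freedom and the programming of the standardized estimate. Both factors are already in the database (SAP 5.2). The change should be fixed before unblinding.
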